#### 13.2.5. Physical Assessment

A physical assessment of height (measured in cm), and weight (measured in kg) will take place at baseline.

#### 13.2.6. Medications

A full list of current medications will be recorded at baseline. Changes and additions will be recorded for the duration of the trial until the trial completion visit, 4 weeks after the last dose of epirubicin.

Details of all chemotherapy, pre-medications and supportive treatments will also be recorded as part of the trial.

Details of concomitant treatments which may interact with enalapril can be found in the SmPC; e.g., non-steroidal anti-inflammatory drugs (NSAIDs), potassium supplements, diuretics, etc.

#### 13.2.7. Blood Pressure

Blood pressure (BP) will be assessed at baseline, prior to taking any blood samples. BP needs to be assessed whilst the patient is sitting. If the first reading provides a systolic value greater than 160mmHg, the test should be repeated on two further occasions, with the patient quiet and seated. If white coat hypertension is suspected, ambulatory BP monitor may be used to avoid inappropriate exclusion from the trial. Severe hypertension on ambulatory BP is defined as 150/95.

All patients will have their BP measured in the same way within 72 hours prior to day 1 of each cycle of chemotherapy and also at the trial completion visit.

For those patients randomised to receive enalapril, BP will also be measured on each of the days that they attend for a dose evaluation visit.

### **13.2.8. Troponin T and Troponin I**

Blood samples will be taken to assess troponin T and troponin I. Full details can be found in the PROACT laboratory manual.

#### **Eligibility blood sample**

At baseline, up to 5mL of blood will be taken in a serum-separation tube (SST) for the troponin T eligibility check. This blood sample will be collected and sent for immediate local processing. If the local processing laboratory finds that the sample collected is haemolysed, a repeat sample will be requested immediately. Serum from this sample will be sent for central analysis at Newcastle Laboratories (Newcastle-upon-Tyne Hospitals NHS Foundation Trust). If the serum sample is not sent on the same day, it will be frozen and transported the following day at -20°C. This baseline serum sample will be received and analysed in real time for Troponin T. The laboratory will confirm the Troponin T result with the site team and this will be recorded in the eCRF. An aliquot of serum from this baseline sample will be stored at -80°C for troponin I analysis at the end of the study.

#### **Blinded end-point blood samples**

After randomisation, up to 5mL of blood will be collected in an SST, processed immediately after collection, stored and transported as described in the PROACT laboratory manual. These samples will be taken within 72 hours prior to the intended start of chemotherapy at cycle 2, 3, 4, 5, 6 and at one month after the last epirubicin dose. These samples will be taken to coincide with standard pre-chemotherapy bloods, where possible. If the local processing laboratory finds that the samples collected are haemolysed, a repeat sample will be requested immediately. If chemotherapy is delayed by the clinical team, further study blood samples for troponin will not be required.

Troponin T will be batch-tested in a blinded manner for this trial and data will be entered into the eCRF by the central laboratory teams.

Troponin I will be batch-tested in a blinded manner at the end of the trial and the result entered into the eCRF by central teams.

Any remaining serum after analysis will be discarded.

The research team will not be made aware of the results of the troponin testing until the end of the trial. The results will not be available for the patients or treating clinicians.

A full chain of custody will be maintained for each sample throughout its lifecycle. The principal investigator at each study site will keep full traceability of collected samples while in storage at site until shipment or disposal and keep records of shipping for each sample. The receiver will acknowledge receipt of each sample and keep full traceability of the samples whilst in storage and during use until used or disposed of.

#### **13.2.9. Urea and Electrolytes (U&Es)**

U&Es (Urea, Na+, K+ and Creatinine) will be assessed at baseline, at each dose evaluation visit (enalapril arm only), and within 72 hours prior to the intended day 1 at the start of chemotherapy at cycle 2, 3, 4, 5, 6 and at one month after the last epirubicin dose.

Samples will be collected, processed and analysed in accordance with local hospital practice, with the results recorded in the eCRF. These blood samples are often taken and tested routinely, if this is the case, and they fit within the windows for the trial, repeat tests specifically for the trial are not needed.

If serum creatinine levels increase by 30 µmol/L over 48-96 hours, or increases to >1.5 times the baseline value, the clinical judgement of the Principal Investigator should be sought, and/or the Chief Investigator, to confirm the action to be taken, which may require a temporary or permanent halt to enalapril (for those in the enalapril group).

#### **13.2.10. Estimated GFR**

Estimated GFR will be assessed at baseline. The recommended method for calculating eGFR is the Modification of Diet in Renal Disease (MDRD) GFR equation. eGFR must be ≥30 mL/min/1.73m^2 at baseline for the patient to be eligible to enter the trial.

#### **13.2.11. Pregnancy Test**

A pregnancy test (urine or blood) must be performed in all female patients of childbearing potential, between the ages of 18 and 50 in the 7 days prior to randomisation. The test must confirm that the patient is not pregnant.

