  - are pregnant or breastfeeding;
  - for patients of childbearing potential only: refusal to use adequate contraception throughout the trial;
  - Previous Herceptin treatment or planned Herceptin treatment within four weeks following anthracycline chemotherapy;
  - any other cancer diagnosis;
  - participation in other interventional medicinal trials in the past 6 months;
  - judgment by the Investigator that the patient should not participate in the study.

---

**Primary Objective:** To establish the effectiveness of the angiotensin-converting enzyme inhibitor (ACEI) enalapril maleate (enalapril) in preventing cardiotoxicity in patients with breast cancer undergoing adjuvant epirubicin-based chemotherapy.

---

**Primary Outcome:** The primary outcome of PROACT is the presence or absence of cardiac troponin T release at any time during epirubicin treatment, and one month after the last dose of epirubicin.

---

**Secondary Outcomes:** Secondary outcomes will focus on the effectiveness of enalapril in preventing cardiotoxicity. These include important measures of cardiac function which relate directly to patient outcomes:

- cardiac function assessed by echocardiogram, including global longitudinal strain (GLS), and measurements of left ventricular ejection fraction (LVEF), at baseline and following completion of anthracycline chemotherapy;
- cardiac troponin I release at any time during adjuvant chemotherapy and one month after the last dose of

---

---

epirubicin;

- adherence to enalapril;
- side effects of enalapril;
- adverse events;
- any anxiety or distress related to trial participation.

---

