## 10. Trial Population

Participants will be recruited from adult patients, due to receive 6 cycles of epirubicin-based adjuvant chemotherapy (total planned dose of epirubicin must be  $>300\text{mg/m}^2$ ) for their breast cancer at recruiting centres, who agree to participate in the trial.

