### 10.2. Exclusion Criteria

- Positive baseline cardiac troponin T ( $\geq 14\text{ng/L}$ );
- known contraindication to ACE inhibitor e.g. renal artery stenosis, severe aortic stenosis;
- are taking, or have a previous intolerance to ACEI (e.g. angioedema);
- patient already taking other agents acting on the renin-angiotensin-aldosterone system e.g. Aliskiren, angiotensin receptor blockers (ARBs), Entresto (sacubitril/valsartan), spironolactone, eplerenone;
- LVEF  $<50\%$ \*;
- estimated GFR  $< 30\text{ mL/min/1.73m}^2$  at baseline;
- hyperkalaemia defined as serum potassium  $\geq 5.5\text{mmol/L}$ ;
- symptomatic hypotension, or Systolic Blood Pressure  $<100\text{mmHg}$ ;
- poorly-controlled hypertension (Blood Pressure  $>160/100\text{mmHg}$ \*\*, or ambulatory BP of  $150/95\text{mmHg}$ );
- previous myocardial infarction;
- known metastatic breast cancer;
- previous exposure to anthracycline chemotherapy;
- are pregnant or breastfeeding
- Previous Herceptin treatment or planned Herceptin treatment within four weeks following anthracycline chemotherapy
- for patients of childbearing potential: refusal to use adequate contraception throughout the trial;\*\*\*
- any other cancer diagnosis;
- participation in other interventional medicinal trials in the past 6 months;
- judgment by the Investigator that the patient should not participate in the study, for example, if the patient is unlikely to comply with study procedures, restrictions, and requirements.

\*<50% as defined by Simpson's biplane method; if absolute measurements are not possible, then a visually normal assessment of LVEF is acceptable for inclusion.

\*\*White coat hypertension is more common, and should be ruled out by an ambulatory blood pressure monitor

\*\*\*Female patients between the ages of 18 and 50 will receive a pregnancy test at baseline.

Adequate methods of contraception are those that can achieve a failure rate of less than 1% per year when used consistently and correctly, such methods include:

- combined (estrogen and progestogen containing) hormonal contraception associated with inhibition of ovulation
  - oral
  - intravaginal
  - transdermal
- progestogen-only hormonal contraception associated with inhibition of ovulation
  - oral
  - injectable
  - implantable
- intrauterine device (IUD)
- intrauterine hormone-releasing system (IUS)
- bilateral tubal occlusion
- vasectomy/vasectomised partner

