## 13. Trial Procedures

### 13.1. Summary of Trial Assessments

	Baseline (up to 6 weeks prior to randomisa- tion)	Day 1 (at least 5 days prior to Cycle 1 Day 1)	Dose evaluation visit 1	Dose evaluation visit 2	Dose evaluation visit 3	Cycle 1, Day 1	Cycle 2, Day 1	Cycle 3, Day 1	Cycle 4, Day 1	Cycle 5, Day 1	Cycle 6, Day 1	Trial Completi- on Visit b)
Consent a)	X											
Demographics	X											
Medical History	X											
Cancer history	X											
Performance Status	X											
NYHA Class	X											
Concomitant medications b)	X	X	X	X	X	X	X	X	X	X	X	X
Physical Assessment (height and weight)	X											
Blood Pressure	X		X	X	X	X	X c)	X				
Troponin T	X d)						X c)	X				
Troponin I	X						X c)	X				
U+Es	X		X	X	X		X c)	X				
eGFR	X											
Pregnancy test e)	X											
Echocardiogram f)	X											X
Eligibility check	X											
Randomisation	X											
Enalapril (intervention group only)		X	X	X	X	X	X	X	X	X	X	
Adherence to enalapril (intervention group only)		X	X	X	X	X	X	X	X	X	X	X
Standard care adjuvant chemotherapy (all patients)						X	X	X	X	X	X	
Adverse Events		X	X	X	X	X	X	X	X	X	X	X
Buccal swab for future research	X											
Blood sample for future research	X							X		X		X
Acceptability of trial interventions assessment									X			X

- a) Consent must be taken prior to baseline assessments and confirmation of eligibility, and within 6 weeks of randomisation.
- b) A list of all medication currently being taken by the patient, including total daily dose, should be recorded at baseline; changes and new medications must be recorded throughout the trial.
- c) All blood samples, including those for troponin T and I, MUST be taken before the next dose of chemotherapy is given; these and blood pressure monitoring can be performed up to 72 hours in advance of the day of chemotherapy.
- d) Troponin T at baseline will be used to assess eligibility
- e) Women between the ages of 18 and 50 must have a negative pregnancy test at baseline, and prior to randomisation and use adequate contraception from consent, throughout the trial.

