## 16.4. Overdose

Patients who take a deliberate overdose of enalapril should be referred for an emergency assessment and withdrawn from the trial.

Accidental overdose will be defined as accidental ingestion of greater than the planned daily dose of enalapril. Enalapril is not usually dangerous in overdose, although most commonly causes hypotension. Patients who are asymptomatic, without hypotension at 5 hours are unlikely to have significant toxicity. In the trial population, medical assessment is recommended for overdose in the following patients who are treatment naïve or have taken more than their daily therapeutic dose:

- Patients aged over 65 years (who are more at risk of complications)
- Patients who are known to have renal impairment
- Patients on treatment with azathioprine, lithium or potassium
- Patients who have ingested >0.7mg/kg

After accidental overdose, the patient should not take further enalapril until discussion with the trial team at the earliest opportunity. The safety and appropriateness of restarting enalapril, including timing, will be considered at the discretion of the PI. A maximum of 7 days interruption will be permitted.

All overdoses will be recorded in the eCRF and noted in the deviation log. Where an overdose fulfils an SAE, then it will be fully described in the SAE report form and follow SAE reporting guidelines (see section 16.5).

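### Minor safety point: every pregnancy-test rule stops at age 50, while the pregnancy exclusion and the section 10.2 contraception criterion have no upper age, and childbearing potential is never defined.

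*Combined protocol and SAP*

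**What the plan says.** The protocol states who is to have a pregnancy test in three places.

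- Section 10.2, in the note marked with three asterisks on the contraception criterion: "Female patients between the ages of 18 and 50 will receive a pregnancy test at baseline".
- Section 13.1, footnote e to the assessment schedule: "Women between the ages of 18 and 50 must have a negative pregnancy test at baseline, and prior to randomisation and use adequate contraception", the contraception to run from consent to the end of the trial.
- Section 13.2.11, the detailed instruction: the test "must be performed in all female patients of childbearing potential, between the ages of 18 and 50 in the 7 days prior to randomisation". It may be on urine or blood and must show that the patient is not pregnant.

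The rules that the test supports are worded differently. Section 10.2 excludes patients who "are pregnant or breastfeeding", with no age attached. It also excludes, "for patients of childbearing potential: refusal to use adequate contraception throughout the trial"; the synopsis says the same, "for patients of childbearing potential only: refusal to use adequate contraception throughout the trial". Neither version names an age.

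Entry has a lower age limit only. Section 10 says "Participants will be recruited from adult patients, due to receive 6 cycles of epirubicin-based adjuvant chemotherapy". Section 16.4 expects older patients on enalapril, since its list for medical assessment after overdose includes "Patients aged over 65 years (who are more at risk of complications").

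**The concern.** A test rule should cover everyone to whom the matching exclusion could realistically apply. Here the exclusion and the section 10.2 contraception criterion depend on pregnancy and childbearing potential, but the test depends on an age band. A woman of 51 who could still conceive meets the terms of the contraception criterion, yet none of the three test rules asks for a test.

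The protocol itself treats pregnancy as incompatible with the study drug. Section 12.2 withdraws a patient who becomes pregnant, and section 16.3 stops enalapril at once. What is at stake is patient safety at entry. The primary outcome, the sample size and the comparison of the arms do not depend on it.

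**Working it through.** There is no planned figure to reproduce, so the check is a comparison of the rules.

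| Rule | Place | Who is covered | Upper age | Timing |
|---|---|---|---|---|
| Pregnancy exclusion | 10.2 | any pregnant patient | none | at entry |
| Contraception criterion | 10.2, synopsis | patients of childbearing potential | none | whole trial |
| Contraception duty | 13.1, footnote e | women 18 to 50 | 50 | from consent, whole trial |
| Test | 10.2 note | women 18 to 50 | 50 | at baseline |
| Test | 13.1, footnote e | women 18 to 50 | 50 | at baseline and before randomisation |
| Test | 13.2.11 | women of childbearing potential, 18 to 50 | 50 | within 7 days before randomisation |
| Withdrawal or stopping for pregnancy | 12.2, 16.3 | any patient | none | on trial |

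**Who is covered.** Counting the three test rules for each group of women:

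- aged 18 to 50, of childbearing potential: 3 of 3;
- aged 18 to 50, not of childbearing potential: 2 of 3 (section 10.2 and footnote e only);
- over 50, of childbearing potential: 0 of 3.

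The last line is the gap. The second line is a smaller inconsistency: two rules test such a woman and the third does not.

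**Does another section close the gap?** Section 13.2 lists the pregnancy test among assessments that may be taken from routine care, and says that those not done routinely must be done for the trial. That sentence names no age range and no time limit. The specific rule in 13.2.11 and the footnoted row of the schedule decide who is tested, so the general sentence does not clearly extend testing past 50.

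**Is the term defined?** No definition of childbearing potential appears in the text available for review.

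**Timing.** The schedule lets baseline run up to 6 weeks before randomisation, 6 × 7 = 42 days, against 7 days in 13.2.11. The written outer limits differ by 42 − 7 = 35 days. They do not conflict, because a test within 7 days also falls within baseline.

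**The case against.** The best defence is that 18 to 50 is the protocol's working stand-in for childbearing potential. Footnote e supports this: it places on women aged 18 to 50 the contraception duty that section 10.2 places on patients of childbearing potential. The section 10.2 note attaches the age band to that same criterion, and the wording of 13.2.11 can be read as a gloss. On this reading the age cut-off is a consistent design choice and the gap disappears. Much of this stands, and it is why the point is conditional. But the protocol never says that the two are equal, and 13.2.11 can equally be read as setting two conditions.

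The second defence is that other safeguards remain, and this stands too. Pregnancy excludes at any age, section 11.3 requires an investigator to confirm eligibility before randomisation, and investigator judgement is itself an exclusion. A site that suspected pregnancy at 51 would have to resolve it first.

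Four stronger readings are tempting, and the documents do not support them.

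- A reader might infer that the protocol lets pregnant women over 50 be randomised. It does not; only the required test is missing.
- A reader might infer that a site may rely on a test up to 42 days old. Section 13.2.11 is binding, and section 13.1 is only a summary of assessments, so a site following the whole protocol is held to 7 days.
- A reader might want a count of women at risk. The documents give no age or menopausal data, so any percentage would be invented. It would also count untested women, and undetected pregnancies would be fewer still.
- A reader might add that the schedule shows no pregnancy test during treatment. That is true for every woman in the trial and has no bearing on the cut-off at 50.

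**Conclusion.** The point holds as a minor safety matter with a cheap remedy. All three test rules end at 50, while the pregnancy exclusion and the section 10.2 contraception criterion have no upper age. Unless the age band is an unstated proxy, a woman over 50 of childbearing potential has no protocol-required test before enalapril.

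The number affected is not given and is probably very small, which is a judgement and not a figure from the documents. The conclusion rests on two readings: that the specific test rules prevail over the general sentence in 13.2, and that childbearing potential means reproductive status and not an age band. If the sponsor intended the proxy, what is left is an undefined term. The 7-day wording is a matter of alignment only.

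**What to change.** Define childbearing potential once, in section 10.2, by reproductive status and without a fixed upper age. Use that term for both contraception and testing, including the contraception duty in footnote e.

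In the section 10.2 note, footnote e and section 13.2.11, put the same rule in place of the 18-to-50 band: a negative urine or blood pregnancy test within 7 days before randomisation for every woman of childbearing potential. This also brings the 7-day limit into the two places that lack it.

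The cost is one definition, matching wording in three places, and a few extra urine tests in women over 50. Women aged 18 to 50 who are not of childbearing potential would no longer need the test that section 10.2 and footnote e now ask of them; for them it serves no safety purpose. The statistical sections need no change.

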#### **13.2.12. Echocardiogram**

Cardiac function will be assessed via transthoracic echocardiography (TTE) at baseline, and 4 weeks following the last epirubicin dose.

All echocardiograms will be assessed by a Core Laboratory, led by [name], and [name] at The James Cook University Hospital. Images will be transferred from the study centre to the Core laboratory in accordance to the PROACT Echocardiogram Manual. [name], [name], and their team, will be blinded to the arm of the study to which patients are allocated.

Local reporting of the TTEs will be as per local hospital practice; the data reported by the Core laboratory (including GLS and LVEF) will be recorded in the eCRF and will be analysed as part of the secondary outcomes for the trial.

The PROACT Echocardiogram Manual provides further guidance to all centres involved in the study, detailing the number, quality and types of images to be acquired, and details of how to send these to the Core Laboratory. Heart rate and sinus rhythm will also be recorded at the time of the echocardiograms.

#### **13.2.13. Swabs**

If consent is given, buccal swabs will be taken at baseline. The samples will be processed into lysis buffer and stored at -20°C for up to one month. The sample will then be transported according to the laboratory manual to Newcastle University where DNA will be extracted. DNA samples will be stored at -80°C until analysis for a maximum period of 15 years following the last patient's last visit (LPLV) in the study, after which time they will be destroyed. Samples will be stored and used until no further analyses are possible or the maximum storage time has been reached.

A full chain of custody will be maintained for each sample throughout its lifecycle. The principal investigator at each study site will keep full traceability of collected samples while in storage at site until shipment or disposal and keep records of shipping for each sample. The receiver will acknowledge receipt of each sample and keep full traceability of the samples whilst in storage and during use until used or disposed of.

#### **13.2.14. Blood sampling for further research**

If consent is given, blood samples for further research will be collected in one SST (up to 5mL) and one EDTA tube (up to 5mL) at the following visits throughout the study: baseline, and within 72 hours prior to intended day 1 at the start of chemotherapy at cycle 3, 5 and at one month after the last epirubicin dose. These should be processed immediately at the local site, divided into four aliquots, stored at -20 °C and transported according to the laboratory manual.

These samples will be stored at Newcastle Laboratories at -80°C until analysis for a maximum period of 15 years following the last patient's last visit (LPLV) in the study, after which time they will be destroyed. Samples will be stored and used until no further analyses are possible or the maximum storage time has been reached.

A full chain of custody will be maintained for each sample throughout its lifecycle. The principal investigator at each study site will keep full traceability of collected samples while in storage at site until shipment or disposal and keep records of shipping for each sample. The receiver will acknowledge receipt of each sample and keep full traceability of the samples whilst in storage and during use until used or disposed of.

